A Phase 3b Multicenter, Single-Arm, Open-Label Safety Study of LY2951742 (galcanezumab) in Patients with Episodic or Chronic Cluster Headache

Rationale:

Galcanezumab is a humanized monoclonal antibody that selectively binds to and neutralizes calcitonin gene-related peptide (CGRP) that has been identified for clinical development in pain conditions relevant to the CGRP pathway such as migraine and cluster headache. The similarities between migraine and cluster headache, the role of CGRP in both disorders, and the clinical efficacy observed with galcanezumab to date for the preventive treatment of migraine support the evaluation of galcanezumab for the treatment of cluster headache.

The aim of this study is to assess the long-term safety and tolerability of galcanezumab 300 mg administered up to once monthly in episodic or chronic cluster headache patients who have completed Study I5Q-MC-CGAL (CGAL) or Study I5Q-MC-CGAM (CGAM).

Objective(s)/Endpoints:

The primary objective of this study is to evaluate the safety of open-label galcanezumab within the context of expected medical practice in eligible patients with episodic or chronic cluster headache. Safety will be assessed using treatment emergent adverse events (TEAEs), serious adverse events (SAEs), as well as suicidal ideation and behaviors utilizing the Columbia-Suicide Severity Rating Scale (C-SSRS).

Summary of Study Design:

Briefly, Study I5Q-MC-CGAR (CGAR) is a Phase 3b single-arm, open-label safety study of galcanezumab 300 mg in outpatients with episodic or chronic cluster headache who completed Study CGAL or Study CGAM. This study will consist of 2 study phases (SP): SP I is the screening phase to confirm patients meet the inclusion/exclusion criteria, and SP II is the open-label treatment phase during which patients can receive galcanezumab 300 mg administered subcutaneously (SC) up to once a month. Within the paradigm of a once-monthly dosing regimen, the decision to dose at each monthly interval will be determined by the investigator.

Treatment Arms and Duration:

One treatment arm: galcanezumab 300 mg administered SC up to once a month as determined by the study investigator based on clinical symptoms and response.

Number of Patients:

[figure not shown]
This is an open-label safety study for patients who previously enrolled in and completed Study CGAL or Study CGAM. Therefore, the sample size is determined by the number of patients completing Studies CGAL and CGAM who choose to enroll in this study.

Statistical Analysis:

Unless otherwise specified, analyses will be conducted on the evaluable analysis set, which includes all enrolled patients receiving at least 1 dose of the investigational product.

The primary analyses will include summaries of TEAEs, SAEs, and suicidal ideation and behaviors assessed by solicited questioning using the C-SSRS.

2. Schedule of Activities

*Approximately 1 week after the 1st dose at Month 0, a Telephone visit will occur (Use Event List G).

**If treatment was halted per protocol during the study, the following procedures: ECG, immunogenicity, PK, hematology, clinical chemistry, HbA_{1c} and urine pregnancy, are to be completed prior to reinitiation of dosing (see Section 5.1 for additional details).

Figure 2.1. CGAR visit flow diagram.

Table 2.1. Schedule of Activities, Protocol I5Q-MC-CGAR

Study Phase	SP I		SP II				
	Dosing Visits			Non-dosing visits			
Events	Event List A	Event List B	Event List C	Event List D	Event List E	Event List F	Event List G
Visit	Visit 1 ^{a,b,c,d}	Month 0 1 st Dose	Month 1	Month 6 and every 6 Months thereafter (e.g., Month 12, 18...)	Months not listed in Event List B, C, or D (e.g., Month 2, 3, 4, 5, 7, 8...)	The first visit after a dose	Dose is not administered; Telephone visit
Informed consent	X						
Inclusion/exclusion criteria	X						
Medical history and pre-existing conditions	X						
Electrocardiogram ^e	X	X		X		X	
Physical examination ^f	X	X	X	X	X	X	
Weight	X			X		X	
Waist and hip circumference	X						
Vitals ^g	X	X	X	X	X	X	
Hematology ^e	X			X		X	
Clinical chemistry ^e	X			X		X	
Urinalysis ^e	X			X		X	

Study Phase	SP I	SP II					
	Dosing Visits				Non-dosing visits		
Events	Event List A	Event List B	Event List C	Event List D	Event List E	Event List F	Event List G
Visit	Visit 1 ^{a,b,c,d}	Month 0 1 st Dose	Month 1	Month 6 and every 6 Months thereafter (e.g., Month 12, 18...)	Months not listed in Event List B, C, or D (e.g., Month 2, 3, 4, 5, 7, 8...)	The first visit after a dose	Dose is not administered; Telephone visit
HbA _{1c} ^e	X			X		X	
FSH	X						
Serum pregnancy ^k	X					X	
Urine pregnancy test ^{e, k} (performed by site)		X		X			
Urine drug screen ^k	X						
Immunogenicity ^e		X	X	X		X	
PK sampling ^e		X	X	X		X	
PGI-I			X	X		X	
EQ-5D-5L	X	X	X	X		X	
Cluster headache status	X	X	X	X	X	X	
C-SSRS/SHSF, SHFU ^h	X	X	X	X	X	X	
AEs	X ⁱ	X	X	X	X	X	X
SAEs	X	X	X	X	X	X	X

Study Phase	SP I	SP II					
		Dosing Visits				Non-dosing visits	
Events	Event List A	Event List B	Event List C	Event List D	Event List E	Event List F	Event List G
Visit	Visit 1^{a,b,c,d}	Month 0 1st Dose	Month 1	Month 6 and every 6 Months thereafter (e.g., Month 12, 18...)	Months not listed in Event List B, C, or D (e.g., Month 2, 3, 4, 5, 7, 8...)	The first visit after a dose	Dose is not administered; Telephone visit
Concomitant medications	X	X	X	X	X	X	
Administer LY2951742 ^j		X	X	X	X		

Abbreviations: AE = adverse event; C-SSRS = Columbia-Suicide Severity Rating Scale; EQ-5D-5L = European quality 5-dimensions 5-levels; FSH = follicle stimulating hormone; HbA_{1C} = hemoglobin A1C; ND = not done; PGI-I = Patient Global Impression of Improvement; PK = pharmacokinetics; SAE = serious adverse event; SHFU = Self-Harm Follow-up Form; SHSF = Self-Harm Supplement Form; V = visit.

- a If the last visit of the parent study is also the first visit of Study CGAR, then ECGs, vitals, weight, hematology, clinical chemistry, urinalysis, HbA_{1C}, and serum pregnancy, C-SSRS, and SHSF/SHFU from the last visit of the parent study will also be used for the first visit of CGAR. All other study procedures in Event List A need to be completed at V1 of CGAR.
- b If the last visit of the parent study is ≤2 weeks from V1 of CGAR, the hematology, chemistry, HbA_{1C}, and urinalysis do not need to be repeated. All other study procedures in Event List A need to be completed at V1 of CGAR.
- c If the last visit of the parent study is >2 weeks from V1 of CGAR, all study procedures in Event List A need to be completed at the first visit of CGAR.
- d After V1, if V2 does not occur within 3 months of V1 (e.g., patient enters V1 in remission), prior to V2 an ECG, hematology, clinical chemistry, urinalysis, urine drug screen, HbA_{1C}, and serum pregnancy must be collected and eligibility confirmed again prior to dosing at V2.
- e If treatment was halted per protocol during the study, the following procedures: ECG, immunogenicity, PK, hematology, clinical chemistry, HbA_{1C} and urine pregnancy, are to be completed prior to reinitiation of dosing (see Section 5.1 for additional details).
- f Directed physical examination only if needed.
- g Vital signs include body temperature, blood pressure, and pulse. Blood pressure and pulse will be measured in triplicate in the sitting position and should be measured prior to blood draws.
- h The C-SSRS and SHSF (SHFU when applicable) will be completed at scheduled and unscheduled office visits.
- i At V1, record AEs that are on-going from the previous trial.
- j Patients should remain in the office for 30 minutes of observation following the first LY2951742 injection of the study; injections of LY2951742 are to occur after all other visit procedures are completed.
- k May be repeated during the study at the discretion of the investigator.

3. Introduction

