5.1. Overall Design

Study CGAR is a Phase 3b single-arm, open-label safety study of galcanezumab 300 mg in outpatients with episodic or chronic cluster headache who completed Study CGAL or Study CGAM.

Please refer to the Protocol Operations Manual for information regarding the schedule of activities, study design, study tools, and patient scenario examples.

The study will consist of 2 SP:

- SP I is the screening phase to confirm patients meet the inclusion/exclusion criteria.
- SP II is the open-label treatment phase during which patients can receive galcanezumab 300 mg administered subcutaneously (SC) up to once a month.

Study Phase I: SP I is the screening phase. Patients will sign an informed consent document prior to completing any study-related screening procedures. SP I is the time from Visit (V)1 to V2. The minimum timeframe for SP1 needs to allow sufficient time for patients to washout of any excluded medications and to review subject eligibility. Visit 1 will be considered complete when the last procedure of the screening assessment for the patient is completed. Once Study CGAR is open for enrollment, potentially eligible patients may enter screening directly from the parent study, CGAL or CGAM. If a patient is not experiencing cluster headache attacks (e.g., in remission) they may wait to enter screening for CGAR until they anticipate experiencing or are experiencing a cluster headache attack. If patients had completed the parent study, CGAL or CGAM, prior to Study CGAR being open for enrollment, potentially eligible patients may still enter screening for Study CGAR. Study procedures for V1 (Event List A) of Study CGAR will be completed as follows:

- If the last visit of the parent study is also the first visit of Study CGAR, then electrocardiograms (ECGs), vitals, weight, hematology, clinical chemistry, urinalysis, hemoglobin A1C (HbA_{1C}), and serum pregnancy, C-SSRS, and Self-Harm Supplement Form/ Self-Harm Follow-up Form (SHSF/SHFU) from the last visit of the parent study will also be used for the first visit of Study CGAR.
- If the last visit of the parent study is ≤ 2 weeks from V1 of Study CGAR, the hematology, chemistry, HbA_{1C}, and urinalysis do not need to be repeated.
- If the last visit of the parent study is > 2 weeks from V1 of Study CGAR, all study procedures in Event List A need to be completed at the first visit of Study CGAR.

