10.3. Statistical Analyses

10.3.1. General Statistical Considerations

Statistical analysis of this study will be the responsibility of Lilly or its designee. Details of statistical analysis methods will be described in the statistical analysis plan (SAP) document.

Efficacy and safety analyses will be conducted on the evaluable analysis set. The evaluable analysis set includes all enrolled patients receiving at least 1 dose of the investigational product.

Baseline will be the time prior to receiving the first dose in this study. Additional baselines may be further outlined in the SAP along with details related to missing data.

Safety and efficacy analyses will be evaluated based on a 2-sided significance level of 0.05 unless otherwise stated. The 95% confidence intervals (CI) for the change from baseline will be presented. There will be no adjustments for multiplicity.

Any change to the data analysis methods described in the protocol will require an amendment ONLY if it changes a principal feature of the protocol. Any other change to the data analysis methods described in the protocol, and the justification for making the change, will be described in the SAP or clinical study report (CSR). Additional exploratory analyses of the data will be conducted as deemed appropriate.

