5.4. General Considerations

General aspects of statistical analyses are described below.

Unless otherwise specified, analyses will be conducted in the GMB-treated population, which includes all patients who are enrolled and receive at least 1 dose of study drug in Study CGAR, and analyses will be presented with 1 treatment arm. Safety analyses will be performed during the GMB-treated time and during the whole open-label treatment phase (SP II), which includes both GMB-treated time plus off-treatment time. GMB-treated time is composed of monthly dosing intervals, that is, the time from a GMB dose to the next monthly visit. The time between the first monthly visit that a dose is not administered and the dosing re-initiation visit is counted as off-treatment time. Baseline will be the time during SP I prior to receiving the first dose in this study. For safety analyses during the open-label treatment phase, any time after the first dose of GMB 300 mg will be considered as postbaseline period no matter if it is during an on-treatment or off-treatment month. For safety analyses during the GMB-treated time, only events that occurred during the GMB-treated time will be considered as postbaseline values.

Statistical analysis of this study will be the responsibility of Lilly or its designee. SAS[®] software will be used to perform most or all statistical analyses.

Any change to the data analysis methods described in the protocol will require an amendment ONLY if it changes a principal feature of the protocol. Any other change to the data analysis methods described in the protocol, and the justification for making the change, will be described in the SAP or clinical study report (CSR). Additional exploratory analyses of the data will be conducted as deemed appropriate.

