5.16.6. Vital Signs and Weight

Vital signs collected during the study include systolic and diastolic blood pressure (BP), pulse, and temperature. BP and pulse measurements will be taken when the patient is in a sitting position. Three measurements of sitting BP and pulse will be collected at approximately 30 to 60 second intervals at every office visit and the 3 sitting BP measurements and 3 pulse values will be averaged and used as the value for that visit.

Table CGAR.5.1 displays the criteria used to define categorical changes of interest in vital signs and weight. The last column of the table displays the patient population for each analysis based on baseline categories. The number and percent of patients meeting these criteria will be summarized.

The criteria to identify patients with treatment-emergent abnormal changes generally consist of 2 parts, an absolute threshold and a change from baseline amount.

- The absolute threshold in the criteria is based on 1) minimum postbaseline when the direction is low; 2) maximum postbaseline when the direction is high.

- The change from baseline amount in the criteria is 1) decrease from baseline to minimum postbaseline when the direction is low; 2) increase from baseline to maximum postbaseline when the direction is high.

The baseline for systolic BP, diastolic BP, and pulse is defined as the last non-missing baseline value during the baseline period.

For categorical changes of interest in temperature and weight, the baseline values are defined below:

- For the analyses of categorical changes of interest in temperature and weight,
 - the baseline is defined as the minimum value during baseline period when the direction is low
 - the baseline is defined as the maximum value during the baseline period when the direction is high

Table CGAR.5.1. Categorical Changes of Interest in Vital Signs and Weight

Parameter	Direction	Criteria	Patients Population defined by Baseline Categories
Systolic BP (mm Hg) (sitting)	Low	≤ 90 and decrease ≥ 20	> 90 ; ≤ 90 ; All patients
	High	≥ 140 and increase ≥ 20	< 140 ; ≥ 140 ; All patients
	PCS High	≥ 180 and increase ≥ 20	< 180 ; ≥ 180 ; All patients
	Sustained Elevation	≥ 140 and increase ≥ 20 at 2 consecutive visits	< 140 ; ≥ 140 ; All patients
Diastolic BP (mm Hg) (sitting)	Low	≤ 50 and decrease ≥ 10	> 50 ; ≤ 50 ; All patients
	High	≥ 90 and increase ≥ 10	< 90 ; ≥ 90 ; All patients
	PCS High	≥ 105 and increase ≥ 15	< 105 ; ≥ 105 ; All patients

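### Weight is not measured at the first dose or repeated after a long wait, so the descriptive 7% weight-change summary misclassifies pre-dose change in late starters

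*Protocol*

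**What the plan says.** **Schedule.** In Protocol Table 2.1, weight is marked under Event List A (V1), Event List D (Month 6 and every 6 months) and Event List F (first visit after a dose). The Month 0 column, Event List B, is blank for weight. The vitals entry at Month 0 does not cover it, since footnote g reads "Vital signs include body temperature, blood pressure, and pulse".

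**Late first dose.** Footnote d, and the matching note in Protocol Section 5.1, apply when V2 falls more than 3 months after V1. The footnote states its trigger as "After V1, if V2 does not occur within 3 months of V1 (e.g., patient enters V1 in remission" and then requires: "prior to V2 an ECG, hematology, clinical chemistry, urinalysis, urine drug screen, HbA_{1C}, and serum pregnancy must be collected". Weight is not in that list. Section 5.1 sets the length of screening only by its end points ("SP I is the time from Visit (V)1 to V2") and gives no upper limit.

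**Baseline.** Protocol Section 10.3.1 says "Baseline will be the time prior to receiving the first dose in this study". SAP Section 5.4 narrows this to "Baseline will be the time during SP I prior to receiving the first dose in this study" and treats all time after the first dose as postbaseline for the open-label phase. For weight, SAP Section 5.16.6 takes the lowest baseline-period value when looking for loss. For gain, "the baseline is defined as the maximum value during the baseline period when the direction is high". For blood pressure, pulse and ECG the SAP instead uses the last non-missing baseline value.

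**Outcome.** SAP Table CGAR.5.1 counts a weight loss or gain of at least 7% in all patients, using the minimum or maximum postbaseline value.

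**The concern.** A change-from-baseline outcome should start from a value close to the first dose. Blood pressure, pulse, temperature and ECG are taken again at Month 0. Laboratory values are not, but footnote d renews them after 3 months. Of the measures with a change criterion in SAP Tables CGAR.5.1 and CGAR.5.2, weight alone gets neither.

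The patients exposed to this are those with a long gap between V1 and the first dose, and footnote d gives entry in remission as its example. Their weight may change while they wait. The SAP then either counts that change as a postbaseline change or lets it cancel a real one. The study has a single arm, so no concurrent control shows how much of the count is background drift. At stake is how one supporting safety summary is read.

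**Working it through.** The plan gives no figure for weight, so there is nothing to reproduce. The check has four steps.

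**1. What the baseline rule becomes.** SAP 5.16.6 takes a minimum or maximum over the baseline period. Only one weight, at V1, is scheduled in that period, so both rules return the V1 value unless a site happens to take another reading. Restricting the analysis to galcanezumab-treated time changes which postbaseline values count, not the baseline.

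**2. Effect on one patient.** Let d be the proportional weight change from V1 to first dose. The on-treatment change needed to be flagged is 0.93/(1+d) − 1 for loss and 1.07/(1+d) − 1 for gain.

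- d = −7%: 0.93/0.93 − 1 = 0%. The patient is flagged for loss with no on-treatment change.
- d = −4%: 0.93/0.96 − 1 = −3.1%. A small on-treatment loss is enough.
- d = +4%: 1.07/1.04 − 1 = +2.9% is enough for a gain, while 0.93/1.04 − 1 = −10.6% is needed for a loss.

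The error therefore runs in both directions.

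**3. Rate among late starters (illustration).** The documents give no weight variability. Assume no drug effect and percent change behaving as a random walk with an SD of 4% or 6% per 12 months. For a single weight, P(gain ≥ 7%) = Φ(−7/SD_t), with SD_t = SD_12 × √(t/12) and t the months since the baseline weight. For a Month 6 weight:

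| Wait before first dose | t | SD 4% | SD 6% |
|---|---|---|---|
| none | 6 | Φ(−2.47) = 0.7% | Φ(−1.65) = 5.0% |
| 3 months | 9 | Φ(−2.02) = 2.2% | Φ(−1.35) = 8.9% |
| 6 months | 12 | Φ(−1.75) = 4.0% | Φ(−1.17) = 12.2% |

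For the 6-month wait, the ratio to no wait is about 2.5 (SD 6%) to 6 (SD 4%).

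The SAP uses the maximum over all postbaseline weights, not Month 6 alone. The quantity needed is P(max over k of (D + S_k) ≥ 7), where D is the pre-dose change and S_k the on-study change at the k-th 6-monthly weight. Simulating the same model with a 6-month wait gives:

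| Follow-up | SD 4%: no wait → wait | Ratio | SD 6%: no wait → wait | Ratio |
|---|---|---|---|---|
| Month 12 | 4.2% → 8.9% | 2.1 | 13.9% → 20.4% | 1.5 |
| Month 24 | 13.8% → 18.1% | 1.3 | 28.0% → 32.2% | 1.15 |

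Loss is symmetric. The ratio falls mainly because on-study drift raises the rate that would be seen even with a Month 0 weight.

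**4. Dilution across the cohort.** The share of late starters is not given. If 10% to 30% waited 6 months and the rest did not wait, the Month 6 rate would move as follows.

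- SD 4%: from 0.7% to 0.7 + 0.1 × 3.3 = 1.0%, up to 0.7 + 0.3 × 3.3 = 1.7%.
- SD 6%: from 5.0% to about 5.7%, up to about 7.1%.

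**The case against.** Most of the case on the other side concerns size and weight of evidence, and much of it stands.

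- **Few patients may be affected.** Protocol Section 5.1 lets patients in remission postpone screening until attacks occur or are expected, which shortens some gaps. It is optional, so it does not close them. An unscheduled pre-dose weight should count, because categorical safety analyses include unscheduled visits, but none is required.
- **A screening value up to 3 months old is this protocol's normal baseline.** Hematology, chemistry, urinalysis and HbA1c also have no Month 0 entry. That is fair: the gap that matters is the missing refresh after a long wait.
- **Weight is a minor outcome.** It is not a primary, secondary or tertiary endpoint. The SAP only summarizes counts and percentages, and it refers fuller safety assessment to integrated analyses described in separate documents.

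A reader might infer three stronger points that the documents do not support.

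- That the whole weight outcome is inflated 2- to 6-fold. That range belongs to one time point, a 6-month wait and assumed SDs, and it ignores the SAP's maximum rule. The later, smaller ratios assume that 6-monthly weights continue. Monthly telephone visits record none, so patients who stop dosing early stay nearer the Month 6 picture.
- That the SAP attributes the changes to galcanezumab. Its wording is treatment-emergent, with no test and no causal claim.
- That reuse of a parent-study weight adds a defect. Footnote a applies only in this case: "If the last visit of the parent study is also the first visit of Study CGAR, then ECGs, vitals, weight, hematology". It is then a same-day weight.

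Many patients also received galcanezumab in the parent study, so a Month 0 weight would not be a drug-naive baseline for them.

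**Conclusion.** The gap is real and follows directly from Table 2.1, its footnotes d and g, and SAP 5.16.6. For patients with a long wait between V1 and first dose, pre-dose weight change is misclassified in the 7% summary, as false flags or as masked changes.

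Its effect on the reported percentages cannot be stated, because neither the number of late starters nor weight variability is given. Under the assumed SDs of 4% to 6% per year, no drug effect and a 6-month wait, the inflation among affected patients is about 2.5- to 6-fold at Month 6. It is about 1.5- to 2.1-fold by Month 12 and 1.1- to 1.3-fold by Month 24, and smaller again across the cohort. For short gaps it matters little. This is a low-priority improvement to a descriptive safety summary, and the primary safety endpoints are not touched.

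**What to change.** **Schedule.** Add a pre-dose weight to Event List B in Table 2.1. At the least, add weight to footnote d and the matching note in Section 5.1. The cost is one scale reading at a visit that already takes place and a small site burden.

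**SAP 5.16.6.** Define baseline weight as the last value before the first dose, as is already done for blood pressure, pulse and ECG. Keeping the minimum/maximum rule with two readings would remove most false flags but under-count true changes. In an illustration with assumed pre-dose and on-treatment SDs of 3% each, V1 alone flags 9.9% of patients, the last pre-dose weight 2.0%, and minimum/maximum over both readings 1.2%.

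**Data already collected.** Report the distribution of the V1-to-first-dose interval, and add a sensitivity summary of the 7% outcome limited to patients with a short interval. This needs no new measurement. A 3-month limit matches footnote d but does not remove all the error: in the illustration above, a 3-month wait still raises the Month 6 rate from 0.7% to 2.2%, or from 5.0% to 8.9%.
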